### 1. INTRODUCTION AND RATIONALE

The sodium-glucose co-transporter 2 (SGLT2) is found primarily in the S1 segment of the proximal tubule of the kidney and accounts for 90% of the glucose reabsorption in the kidney in order to maintain appropriate glucose levels. SGLT2 transports one ion of Na+ per molecule of glucose. Because Na+ is actively extruded by Na/K-ATPase, the extracellular Na+ concentration substantially exceeds the intracellular concentration. Movement of Na+ down its electrochemical gradient provides the energy required for active transport of glucose. SGLT2 inhibitors reversely inhibit the SGLT2-transporter, leading to an increase in urinary glucose and sodium excretion by reducing glucose reabsorption in the renal proximal tubule. Initial relatively short-term studies (up to 52 weeks) have shown that SGLT2 inhibitors exert beneficial effects on multiple cardiovascular risk markers including HbA1c, blood pressure, body weight, and uric acid. Large clinical trials have shown that SGLT2 inhibitors reduce the risks of heart failure and kidney failure in patients with (or without) type 2 diabetes mellitus (T2DM).

Persistent increased albuminuria is an established risk marker for development of chronic kidney disease and cardiovascular disease events in patients with or without type 2 diabetes. Prior studies have shown that SGLT2 inhibitors reduce the urine albumin-to-creatinine ratio (UACR). These UACR-lowering effects of SGLT2 inhibitors tend to be greater with higher levels of baseline UACR. Prior studies have shown that the SGLT2 inhibitor dapagliflozin reduces UACR in patients with T2DM. The UACR reduction achieved with dapagliflozin was independent of concomitant changes in HbA1c, blood pressure, eGFR or uric acid, suggesting a direct mechanism of action.

More recently, the DAPA-CKD trial reported the efficacy and safety of dapagliflozin in 4,304 patients with chronic kidney disease with or without type 2 diabetes. The trial demonstrated that dapagliflozin significantly reduced the risk of kidney and cardiovascular endpoints, prolonged survival and reduced the UACR. Furthermore, dapagliflozin was well tolerated in keeping with the established safety profile. No major hypoglycemic events were reported in these patients.

Despite the efficacy of SGLT2 inhibitors to lower cardiovascular risk markers and slow the progression of kidney function decline and prevent cardiovascular events on a population level, there are still many patients who experience clinically relevant outcomes such as dialysis, kidney transplantation or myocardial infarctions while receiving

dapagliflozin or other SGLT2 inhibitors. For example, in the abovementioned DAPA-CKD trial, 197 patients receiving the SGLT2 inhibitor dapagliflozin experienced the primary composite kidney outcome during 2.4 years follow-up, indicating that these patients were sub-optimally protected. This suboptimal protection is likely caused (at least in part) by sub-optimal response to dapagliflozin. Indeed, analyses from parallel-group trials with dapagliflozin have reported a large variation in UACR (or blood pressure or body weight changes) between individual patients in response to dapagliflozin, suggesting that the degree of benefit and response to dapagliflozin substantially varies among individual patients.

However, it should be noted that randomized parallel group placebo controlled clinical trials are used to test the efficacy and safety of new interventions on a population level but do not assess the efficacy of a drug for the individual. Thus, although analyses from parallel group trials have shown variation between patients in response in UACR or blood pressure to dapagliflozin, it cannot be excluded that this variation is due to measurement or temporal random variation. Alternative trial designs are needed and better suited to evaluate the individual response to dapagliflozin. Various clinical trial designs have been developed that better account for the variability between patients than the traditional randomized parallel group double blind controlled trial. The N=1 clinical trial design specifically allows for assessment of drug efficacy and safety at an individual level. In a N=1 trial, the same patient is exposed multiple times in random order to an active compound or placebo intervention in order to directly estimate the effect of the intervention for each individual. The advantage of a N=1 trial is that the efficacy of the intervention is vetted for the actual patient, thereby increasing patient participation and engagement and making the results of the study directly applicable to the participant. Thus, categorizing patients as responders or non-responders by comparing their values with those at baseline is arbitrary and inefficient since the observed change does not guarantee that the patient is responding to the drug. A N=1 trial with the same patient exposed twice to active medication and placebo is the appropriate design to test the individual drug response.

We therefore propose a N=1 trial determining the UACR response to dapagliflozin for each individual specifically. We furthermore hypothesize that the change in UACR in response to dapagliflozin is reproducible upon re-exposure and reflects a true pharmacological response rather than random variation whereas during placebo treatment changes in UACR are thought and do not correlate. A retrospective analysis

from a cross-over study in non-diabetic kidney disease where patients were exposed twice to an ACE inhibitor or Angiotensin Receptor Blocker supports this notion as in that study a strong correlation between the response during the first and second exposure was observed (correlation coefficient between 0.7 and 0.9).

### 2. OBJECTIVES

- Primary:
  - To determine the individual response to the SGTL2 inhibitor dapagliflozin in urine albumin-to-creatinine ratio (UACR)
- Secondary:
  - To determine the individual response to the SGLT2 inhibitor dapagliflozin in:
    - Systolic blood pressure
    - Body weight
    - eGFR
    - Fasting plasma glucose

### 3. STUDY DESIGN

A randomized placebo-controlled double-blind cross-over N=1 trial in subjects with type 2 diabetes with albuminuria >20 mg/g (2.26 mg/mmol).

### Study execution

The trial will be performed in the remote setting. In a conventional clinical trial, patients have to visit the hospital/clinic multiple times for health check-ups and blood and / or urine collections. This may complicate the feasibility of the trial since not all patients are willing to frequently visit the clinic, which hampers recruitment. In addition, patients may drop out during the trial since the time investment and burden of study visits is higher than originally expected. With the introduction of digital technologies and wearable devices, it becomes possible to assess patients remotely – while they are at home. If used in a clinical trial, it could significantly reduce the number of study visits, time investment for patients, and increase the operational processes of clinical trial conduct.

Some healthcare providers and IT suppliers already offer patients the opportunity to create and manage a personal health record at a central privacy secured server. More and more patients are also keeping their own records, but the scope for combining and sharing all these records is still somewhat limited. Based on a strong believe that people play a vital role in their own health, various parties in the healthcare sector have taken the initiative to set up special platforms to offer people more control over their own health. In this study, we will use such an online platform (Selfcare). Selfcare creates a personal health environment (PHE), a digital tool in which patients can store all their health data in a safe, privacy secured, and independent manner. Up to now, health data has not always been easily accessible, but this PHE allows patients to safely compile and share their own health information online with physicians and researchers.

To take advantage of these developments we will perform this study using digital technologies and ask patients to collect study data at home.

### Study design

Subjects with UACR >20 mg/g (2.26 mg/mmol) with a diagnosis of type 2 diabetes who meet the inclusion criteria will be invited for screening (day -14). After the screening visit, eligible patients will proceed to a second visit (day -7). Patients will be randomly assigned to a cross-over study consisting of two periods of 1-week treatment with dapagliflozin and two periods of 1-week treatment with placebo in random order with a 1-week wash-out

period between every treatment period to avoid cross-over effects. Based on a prior study, effects of dapagliflozin on UACR, blood pressure, body weight, fasting plasma glucose and eGFR were fully present after 4 days. We will therefore ask patients to collect urine after 3, 5, 6, and 7 days. Due to day-to-day variation in UACR we are collecting multiple urine samples to increase precision and therefore collect urine at 3, 5, 6, and 7 days. We will also collect urine after 1 day to further delineate the time-course of the response to dapagliflozin and assess if the treatment effect on UACR is directly present after 1 day. Blood pressure and body weight will be recorded and blood samples will be taken at the time points described below and in the table. Overall, a 1-week treatment period is considered sufficient to detect effects on primary and secondary outcomes.

Since data collection will be performed at home using wearable devices and digital technologies, instructions will be provided during the second visit to perform data collection and study procedures at home. Data collection and measurements will be performed in each treatment period as indicated in Figure 1. Bottles with smart caps that allow real-time monitoring of adherence, blood pressure monitors, body analysis scales and study medication will be provided at the second visit. At the second visit, patients receive four numbered bottles with seven tablets in each bottle, according to their randomized treatment schema. Patients will be instructed to take the study medication once daily, in the morning.

### Measurements:

- First morning void urine collections for measurement of UACR, sodium, potassium, urea, and osmolality will be performed at:
  - o Day -7, -3, -2 and -1
  - o Day 1, 3, 5, 6 and 7 of the active periods
  - Day 3, 5, 6 and 7 of the wash-out periods
- Ambulatory blood pressure will be measured by the patients themselves at home at:
  - o Day -7, -3, -2 and -1
  - o Day 1, 3, 6 and 7 of the active periods
  - Day 6 and 7 of the wash-out periods
- Ambulatory body weight will be measured by the patients themselves at home at:
  - Day -7, -3, -2 and -1
  - o Day 1, 3, 5, 6 and 7 of the active periods

- o Day 3, 5, 6 and 7 of the wash-out periods
- Capillary blood samples for measurement of creatinine, CRP, lipid profile, HbA1c, uric acid, glucose and NT-proBNP will be taken at:
  - Day -7 (under supervision during the second visit) and -1
  - o Day 1, 6 and 7 of the active periods
  - Day 6 and 7 of the wash-out periods

A venous blood sample will also be taken during the second visit in order to compare the clinical chemistry assessments in capillary blood with those measured in venous blood samples.

- Medication will be provided in bottles with smart caps that allow real-time monitoring of adherence.
- Dapagliflozin will be measured by a validated liquid chromatography-mass spectrometry (LC-MS/MS) analysis at day 7 of every active period in capillary blood samples to assess treatment adherence.
- Telephone calls will be made at day 3 and 6 of the first two treatment periods to assess compliance with study procedures.

Questionnaires consisting of 6 multiple choice questions and 2 open questions will be used to assess patient experience and satisfaction to guide and inform future trials and use in clinical practice.

Figure 1: Study design

	Screening visit	Run-i	n p	erio	d	Pe	erio	d 1			W	ash	-OL	it	Period 2/3/4						Wash-out			
Days	-14	-7 (2nd visit)	3	2	1	1	3	5	6	7	3	5	6	7	1	3	5	6	7	3	5	6	7	
Urine samples* (PeeSpot)		X	Х	Х	Х	Х	Х	Х	X	X	X	X	X	X	X	X	X	X	Х	X	X	Х	х	
Blood Pressure		Х	Х	Х	Х	Х	Х		Х	X			Х	Х	Х	Х		Х	Х			Х	Х	
Body weight		Х	Х	Х	Х	Х	Х	Х	Х	Х	Х	Х	Х	Х	Х	Х	Х	Х	Х	Х	Х	Х	Х	
Blood samples** (Hem-Col)		х			Х	Х			Х	Х			Х	Х	Х			Х	Х			Х	Х	
Glucose (Strips)		Х			Х	Х			Х	Х			Х	Х	Х			Х	Х			Х	Х	
Treatment adherence						Х	Х	Х	Х	Х	Х	Х	Х	Х	Х	Х	Х	Х	Х	Х	Х	Х	Х	

18

(MEMS)												
Dapagliflozin concentration (LC-MS/MS)					Х					Х		
Questionnaire												Х

\* UACR, sodium, potassium, urea, and osmolality will be measured

Patients connect their blood pressure monitor and body analysis scale to the corresponding mobile application, which in turn is linked to Selfcare platform. In this way, data will be automatically transferred to Selfcare platform. Patients can also register adverse events in Selfcare. Selfcare creates a personal health environment (PHE), a digital tool in which patients can store all their health data in a safe and independent manner. These data are integrated on a single independent platform. This unique dynamic dashboard forms a reliable basis on which health data can be monitored. At the end of the study, blood pressure and body weight data will be downloaded from Selfcare and along with the biochemical data measured in the central laboratory incorporated in the database.

Selfcare provides the best possible data protection. Selfcare meets the Dutch standard for information security in the healthcare sector (NEN 7510), which relates to the formulation, registration and monitoring of information security. This standard entails: 'Ensuring the availability, integrity and confidentiality of all information needed to provide patients with responsible care.'

Selfcare users have full ownership of their personal health data at all times. Only if the user gives explicit consent, third parties can be granted access to the data. Communication with peers in the in the community and data exchange (if permitted) takes place in a secure environment. Selfcare guarantees privacy whether a patient uses a computer, tablet or smartphone.

When users open Selfcare dashboard from a new device, they are asked to provide a second piece of information (in addition to their username and password) to prove their identity. This is an additional step taken by Selfcare to prevent abuse and provide personal safety.

Selfcare uses HTTPS, a protocol that is used for the secure handling of request between a client (browser) and server (web server). Data are encrypted, making it

\*\*Creatinine, CRP, lipid profile, HbA1c, uric acid, and NT-proBNP will be measured

virtually impossible for someone without proper authorization to access the data. The selfcare servers are hosted at a national level by independent foundations to ensure privacy.

The Selfcare data are subjected to independent supervision by leading authorities in the field of privacy and patient protection. All personal user data are stored on a server, which is located in the country of registration. Ownership of this server lies with a legal entity that is separated from the commercial organization Selfcare. This means that the data are never accessible to third parties and can never be sold to third parties. This ensures that only the end user determines what happens to his or her data.

### 4. STUDY POPULATION

### 4.1. Population (base)

The study population will consist of adult male and female patients with UACR >20 mg/g (2.26 mg/mmol) with T2DM treated in primary or secondary healthcare. Subjects will be recruited via general practitioner practices or via the outpatient clinic of the Department of Internal Medicine of the Ziekenhuisgroep Twente, Almelo.

#### 4.2. Inclusion criteria

In order to be eligible to participate in this study, a subject must meet all of the following criteria:

- Age ≥18 years
- Diagnosis of type 2 diabetes mellitus
- Urinary albumin-to-creatinine ratio >20 mg/g (2.26 mg/mmol)
- eGFR >30 ml/min/1.73m^2
- Willing to sign informed consent

### 4.3. Exclusion criteria

A potential subject who meets any of the following criteria will be excluded from participation in this study:

- Diagnosis of type 1 diabetes
- Prior treatment with SGLT2 inhibitor in the four weeks prior to randomization
- History of severe hypersensitivity or contraindications to dapagliflozin
- Unable to monitor blood pressure / body weight or handle digital technologies
- History of non-adherence to medical regimens or unwillingness to comply with the study protocol
- Participation in any clinical investigation within 3 months prior to initial dosing
- Unstable or rapidly progressing renal disease
- Severe hepatic impairment (Child-Pugh class C) as determined by the treating physician.
- Active malignancy

 Any medication, surgical or medical condition which might significantly alter the absorption, distribution, metabolism, or excretion of medications including, but not limited to any of the following:

- History of active inflammatory bowel disease, within the last six months.
- Major gastrointestinal tract surgery as decided by the treating physician
- Pancreatitis within the last six months.
- Evidence of serious hepatic disease as determined by the treating physician
- Evidence of urinary obstruction or difficulty in voiding at screening.
- Confirmed lactose intolerance demonstrated with a lactose intolerance test.
- Donation or loss of 400 mL of blood within 8 weeks prior to initial dosing
- History of drug or alcohol abuse within the 12 months prior to dosing, or evidence of such abuse as indicated by the laboratory assays conducted during the screening
- Any surgical or medical condition, which in the opinion of the investigator, may place the patient at higher risk from his/her participation in the study, or is likely to prevent the patient from complying with the requirements of the study or completing the study.
- Current pregnancy or breast feeding / attempting to conceive.
- Women of childbearing potential (WOCBP):
  - WOCBP who are unwilling or unable to use an acceptable method of contraception to avoid pregnancy throughout the study and for up to 4 weeks after the last dose of study drug in such a manner the risk of pregnancy is minimized.
  - WOCBP must have a negative serum or urine pregnancy test result (minimum sensitivity 25 IU/L or equivalent of HCG) within 0 to 72 hours before the first dose of study drug.

WOCBP comprises women who have experienced menarche and who have not undergone successful surgical sterilization (hysterectomy, bilateral tubal ligation, or bilateral oophorectomy) or who are not post-menopausal (see definition below). The following women are WOCBP:

 Women using the following methods to prevent pregnancy: oral contraceptives, other hormonal contraceptives (vaginal products, skin patches, or implanted or injectable products), or mechanical products such as intrauterine devices or barrier methods (diaphragm, condoms, spermicides).

- Women who are practicing abstinence.
- Women who have a partner who is sterile (e.g. due to vasectomy).

### Post-menopause is defined as:

- Women who have had amenorrhea for ≥12 consecutive months (without another cause) and who have a documented serum follicle-stimulating hormone (FSH) level >35 mIU/mL.
- Women who have irregular menstrual periods and a documented serum FSH level >35 mIU/mL.
- Women who are taking hormone replacement therapy (HRT).

### 4.4. Sample size calculation

The sample size for this study is based on the hypothesis that the response to dapagliflozin is reproducible upon re-exposure and thus correlates between the first and second exposure while no correlation will be detected during placebo patients. A prior retrospective study found that during intervention in the reninangiotensin-system responses in proteinuria correlate with correlation coefficients ranging between 0.7 to 0.9.9 Since this was a retrospective study, we assume a more conservative correlation coefficient of 0.6. A sample size of 20 patients provides >80% power (alpha 0.05) to detect a correlation coefficient of 0.6.

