#### 10. STATISTICAL ANALYSIS

#### 10.1. Primary study parameter(s)

The change from baseline in UACR will be calculated using the values collected at day 5, 6 and 7 of each treatment and wash-out period. Because of the skewed distribution UACR will be log-transformed before analysis. The geometric mean of these 3 values (at baseline to end of treatment) will be calculated as log(UACRend/UACRbaseline) and the geometric mean change from baseline will be determined.

The study has two cycles for two treatment periods (dapagliflozin and placebo). For calculation of response, the difference in UACR change between dapagliflozin and placebo will be calculated during the first and second cycle. To this end a linear mixed effects model with random intercepts and random slopes for treatment will be used to determine the response during each period. Fixed effects include treatment sequence, and treatment cycle. Baseline log transformed UACR may be added as covariate. Appropriate contrasts will be implemented to assess the placebo substracted response during the first and second cycle and to correlate the placebo adjusted UACR responses to dapagliflozin (fitted on the log-scale) during the two treatment periods. The variance-covariance pattern of the mixed effects model is assumed to be unstructured. If the model does not converge less stringent models will be considered.

To determine if there is within individual variation in treatment response, we will fit a linear mixed model with correlated random intercepts and random slopes for treatment and include treatment period as a fixed effect. Subsequently, we will compare (using a maximum-likelihood ratio fit test) this model against a random intercept only model with treatment and treatment period as fixed effects.

In an additional supportive analysis, we will also dichotomize response. If the placebo adjusted difference in both cycles is greater than 20% in favor of dapagliflozin (using the linear mixed effects model), the patient will meet the response definition. We will then perform a McNemar test for the proportion of concordant response (response during the two cycles or no response during

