#### Frequentist linear mixed effects analysis:

In addition to this Bayesian approach, we will also utilize a frequentist approach to determine the response on UACR during each period. To estimate this response a linear mixed effects model with random intercepts and random slopes for treatment will be used. Fixed effects include treatment sequence, and treatment cycle. Baseline log-transformed UACR may be added as covariate. Appropriate contrasts will be implemented to assess the placebo subtracted response during the first and second cycle and to correlate the placebo adjusted UACR responses to dapagliflozin (fitted on the log-scale) during the two treatment periods. The variance-covariance pattern of the mixed effects model is assumed to be unstructured. If the model does not converge less stringent models will be considered.

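### The >80% power is stated for a correlation of 0.6 that reads as dapagliflozin versus dapagliflozin, but the plan correlates placebo-adjusted responses, where the same 0.6 gives less power

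*Combined protocol and SAP*

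**What the plan says.** Protocol 4.4, repeated in SAP 3.2, sizes the trial on reproducibility, namely "the response to dapagliflozin is reproducible upon re-exposure and thus correlates between the first and second exposure". For placebo, the same sentence expects no such correlation. The assumed value is lowered from coefficients of 0.7 to 0.9 in an earlier retrospective study of renin-angiotensin-system intervention: "Since this was a retrospective study, we assume a more conservative correlation coefficient of 0.6". The conclusion is "A sample size of 20 patients provides >80% power (alpha 0.05) to detect a correlation coefficient of 0.6". Protocol section 1 describes the source as a cross-over study in which patients were exposed twice to an ACE inhibitor or angiotensin receptor blocker. Placebo subtraction is not mentioned.

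Protocol 10.1 defines response as the dapagliflozin-minus-placebo difference in log-UACR change within each cycle. It and the SAP's frequentist section use mixed-model contrasts "to correlate the placebo adjusted UACR responses to dapagliflozin (fitted on the log-scale) during the two treatment periods". On the baseline, Protocol 10.1 leaves a choice open: "Baseline log transformed UACR may be added as covariate". The SAP repeats this option.

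Neither document gives a variance for the dapagliflozin or placebo changes, or converts 0.6 to the placebo-adjusted scale. Neither analysis section computes a placebo-placebo correlation.

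**The concern.** The power statement and the planned correlation concern different quantities. If placebo changes do not correlate between cycles, each one is noise as far as reproducibility is concerned. Subtracting it leaves the covariance between cycles unchanged and increases the variance of each cycle's response. The correlation to be tested is then smaller than the one used for the power.

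Reproducibility on re-exposure is the hypothesis that sizes the trial, and the correlation is the only quantity for which power is given. If its true power is well under 80%, a non-significant correlation could be taken as evidence that response is not reproducible when it is a likely result under the sponsor's own assumption. The hypothesis also has a placebo half, which the analysis sections do not estimate.

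**Working it through.** **Inputs.** From the documents: N=20 (withdrawals are replaced so that twenty complete, Protocol 8.5), alpha 0.05, on-drug correlation 0.6, placebo correlation 0. Assumed: two-sided test (sidedness is not stated), an ordinary correlation test, and a noise ratio k.

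**1. The stated figure.** Fisher z power is Φ(atanh(r)·√(N−3) − 1.96). With r=0.6, atanh(0.6)=0.693 and √17=4.123, so power = Φ(2.858 − 1.960) = Φ(0.898) = 81.5%. An exact bivariate-normal calculation gives 83.6%. The claim of >80% reproduces for r=0.6.

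**2. Conversion to the placebo-adjusted scale.** Scale the dapagliflozin change to total variance 1 and write it as S + e, where S is the reproducible part, Var(S)=0.6 and Var(e)=0.4. Let the placebo change be independent noise with variance 0.4k. The difference within a cycle has variance 0.6 + 0.4 + 0.4k, and the covariance between cycles is still 0.6. Hence

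r_adj = 0.6 / (1 + 0.4k).

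| k | r_adj | Power, N=20, two-sided (Fisher) |
|---|---|---|
| 0 | 0.600 | 81.5% |
| 0.25 | 0.545 | 71% |
| 0.5 | 0.500 | 62% |
| 1 | 0.429 | 47% |
| 1.5 | 0.375 | 37% |
| 2.5 | 0.300 | 25% |

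At k=1 the exact method gives 48.9% and simulation 48.5%. One-sided power there is 60 to 62%. At k=2.5 the placebo variance equals the total dapagliflozin variance (0.4 × 2.5 = 1).

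**3. When 80% survives.** The correlation needed is tanh((1.960 + 0.842)/4.123) = 0.591. Solving 0.6/(1 + 0.4k) = 0.591 gives k ≈ 0.04.

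**4. Other on-drug values at k=1.** Here r_adj = r/(2−r). On-drug 0.7 gives 0.54 and 70%. On-drug 0.8 gives 0.67 and 91%.

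**5. Baseline as covariate, at k=1 and on-drug r=0.6.** Let ρ be the within-patient correlation between the period's baseline and end values, and σ² the within-patient variance of one such value. The noise variance of the dapagliflozin-minus-placebo contrast is 4(1−ρ)σ² with change scores and 2(1−ρ²)σ² with the baseline as covariate, a ratio of (1+ρ)/2. The change-score noise of 0.8 becomes 0.4(1+ρ), so r_adj = 0.6/(1 + 0.4ρ).

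| ρ | r_adj | Power (Fisher) |
|---|---|---|
| 0 | 0.60 | 82% |
| 0.3 | 0.54 | 69% |
| 0.5 | 0.50 | 62% |

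The plain change score has 47% throughout. The optional covariate therefore moves power by 15 to 35 percentage points over this range of ρ.

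**The case against.** **0.6 may already be placebo-adjusted.** Protocol 10.1 defines response as the dapagliflozin-placebo difference. If Protocol 4.4 uses the word in that sense, >80% stands. This cannot be excluded. It is the less natural reading, because 4.4 sets a separate expectation for placebo, which has little purpose once placebo has been subtracted. Either way, the text must say which is meant.

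**Equal noise is not in the documents.** A reader might infer that power is simply 47%. That figure needs k=1. The value is plausible, since the patients, sampling days and period length are the same, but no variance is given. The range is the proper result; only the direction is firm.

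**The analysis is a mixed model.** The contrasts come from a model with one random treatment slope per patient, so a simple correlation is an approximation. That stands as a limit on the figures. It does not rescue the stated power, which reproduces as an ordinary correlation test.

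**The SAP puts Bayesian analyses first.** True; the correlation belongs to an additional frequentist analysis. But SAP 3.2 still justifies N by it and gives no operating characteristics for the Bayesian models.

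**Two stronger readings fail.** A reader might infer that 0.6 is not conservative, because at k=1 a placebo-adjusted 0.6 needs 0.75 on drug, inside the cited 0.7 to 0.9. The documents do not say whether those coefficients were themselves placebo-subtracted, so this cannot be concluded. A reader might also infer that nothing planned separates drug response from random variation. Protocol 10.1 and the SAP compare a random-slope model with a random-intercept model, and the SAP's heterogeneity section adds a treatment-by-subject interaction. In the model above with k=1, an F-test of that interaction has about 75% power: the variance ratio is (0.6 + 0.4)/0.4 = 2.5 on 19 and 40 degrees of freedom.

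**Conclusion.** The concern holds in conditional form. As Protocol 4.4 and SAP 3.2 most naturally read, >80% belongs to the unadjusted correlation of two dapagliflozin exposures and does not carry over to the placebo-adjusted correlation that is planned. With on-drug r=0.6 and plain change scores, power is about 71% down to 25% for k from 0.25 to 2.5. With the period baseline as covariate, it is about 62% to 82% at k=1 for ρ from 0.5 to 0. These figures assume independent placebo noise, a two-sided test and a simple-correlation approximation to the mixed-model contrasts. If the sponsor confirms that 0.6 was placebo-adjusted, the power figure is right and only the wording needs correcting.

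**What to change.** - In Protocol 4.4 and SAP 3.2, state which correlation 0.6 refers to, the sidedness of the test, and the assumed variances of the dapagliflozin and placebo changes. Restate power for the placebo-adjusted correlation as a range conditional on k.
- Replace the optional baseline term in Protocol 10.1 and the SAP frequentist section with a fixed rule on whether the period's own baseline log-UACR is a covariate. Quote power for the version chosen; the change-score figures do not describe a covariate-adjusted analysis.
- Add the dapagliflozin-dapagliflozin and placebo-placebo correlations, each with a confidence interval, as a supportive analysis, so that both halves of the stated hypothesis are estimated.

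The cost is a less favourable stated power and minor edits to the protocol and SAP. No extra patients or measurements are needed.
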